1.6 The decision to initiate dialysis is doctor-driven

Davison et al. conducted a survey, asking the following question (Table 4) among 584 patients with chronic kidney disease stages 4 and 5 as they presented to dialysis, transplantation or predialysis clinics in a Canadian, university-based renal program:²⁷

“If you are currently receiving dialysis, why did you choose dialysis over conservative care (no dialysis)?”

Your doctor’s wish:	51.9%
Your own personal wish:	34.2%
Your family’s wish:	13.9%

Table 4: Excerpt from a survey on end-of-life care preferences and needs in patients with chronic kidney disease.²⁷

The response to the question asked by Davison et al. suggests that the decision to be treated with dialysis reflects physicians’ and family members’ preferences rather than personal choice.²⁷ This opens room for the possibility that women are under-represented in the dialysis population, because doctors might be more reluctant to initiate renal replacement therapy in women than in men.

1.7 Sex-specific differences in chronic kidney disease progression and death risk before the start of dialysis

The effect of sex on the progression of renal disease has been a matter of debate, until Neugarten et al., in a meta-analysis of 68 published studies, were able to show that men have a more rapid decline of renal function than women.²⁸ However, of the eight studies that were selected for meta-analysis²⁹⁻³⁶, the association between sex and the rate of fall in glomerular filtration rate was attenuated in one study and became non-significant after adjusting for differences in blood pressure, proteinuria and high density lipoprotein cholesterol.²⁹ Moreover, two studies^{33, 34} not only used decline in glomerular filtration rate, but also end stage renal failure as an outcome in order to define “progression to end stage renal disease”. This analytical strategy has been shared by a recent study conducted on 185,431 individuals in Austria, which found an increased risk of end stage renal disease, as defined by initiation of renal replacement therapy, for men.³⁷ Clearly, if women were to initiate dialysis later, or not at all, in comparison to men, the bias that might be introduced by a sex-dependent decision to initiate renal replacement therapy would be carried over into the aforementioned analyses. Thus the progression in women might be underestimated due to the inclusion of dialysis initiation in the calculations.

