Doctor level:

In your chronic kidney disease clinic

1. How many men (a) and how many women (b) were registered in the year 2016?
2. According to the first lab result that was taken in 2016, how many men (a) and how many women (b) were in chronic kidney disease stage 4, 3a, 3b, and 2?
3. How many times did the registered men (a) and the registered women (b) have their labs checked and saw the doctor during the year 2016? Please subdivide also by chronic kidney disease stage.
4. How many men (a) and how many women (b) have you informed they will likely need renal replacement therapy (RRT) in the next 12 months?
5. How many men (a) and how many women (b) already have a fistula, and how many have a graft for vascular access?
6. How many men (a) and how many women (b) have you informed about preemptive transplantation as an option for RRT?
7. How many men (a) and how many women (b) have you informed about peritoneal dialysis as an option for RRT?
8. How many men (a) and how many women (b) have you informed about hemodialysis as an option for RRT?
9. How many men (a) and how many women (b) ended up on RRT (HD, PD or preemptive transplantation) during the year 2016?
10. How many men (a) and how many women (b) did you consider end stage and thus in need of undergoing RRT in 2016?
11. How many men (a) and how many women (b) refused RRT in 2016 despite your advice?
12. Among those whom you considered end stage in the year 2016, in how many men (a) and how many women (b) was the decision to withhold or not do RRT mutual (taken by doctor and patient together)?
13. How many men (a) and how many women (b) started RRT in 2016 against your advice?
14. How would you judge your own decision making regarding RRT initiation
 - a) Influenced by patient sex, with men more likely to start RRT
 - b) Influenced by patient sex, with women more likely to start RRT
 - c) Not influenced by patient sex

To obtain adequate data, a reimbursement based on the number of patients seen by the center will be offered to the medical director of the outpatient clinic in December 2016. A specific plan on how to arrive at answering the questions correctly must be submitted; in principle, this plan should encompass several meetings with the outpatient clinic doctors in early 2017, in order to obtain an answer from all of them together (only question 14 must be individually answered).

Patient level:

1. I am a man (a), a woman (b).
2. My age is ... years.

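### The doctor form counts need for RRT only by the doctor's own judgement and omits stage 5, so rates per patient judged end stage can mask or reverse under-labelling of women

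*Combined protocol and SAP*

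**What the plan says.** The hypothesis in section 2.3 is that decisions about starting RRT differ by patient sex. Section 1.6 names one mechanism: "doctors might be more reluctant to initiate renal replacement therapy in women than in men". The doctor form asks each clinic for totals by sex for 2016. The relevant items are:

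- Question 1: patients registered.
- Question 2, at the first laboratory result of the year: "how many men (a) and how many women (b) were in chronic kidney disease stage 4, 3a, 3b, and 2". Stage 5 is not listed.
- Question 9: "How many men (a) and how many women (b) ended up on RRT (HD, PD or preemptive transplantation) during the year 2016". This covers all starts.
- Question 10: "How many men (a) and how many women (b) did you consider end stage and thus in need of undergoing RRT in 2016". No laboratory criterion is attached.
- Question 11: "How many men (a) and how many women (b) refused RRT in 2016 despite your advice". This presupposes that the doctor advised RRT.
- Question 12 is tied to the group in question 10: "Among those whom you considered end stage in the year 2016, in how many men (a) and how many women (b) was the decision to". It asks about decisions against RRT that doctor and patient shared.
- Question 13: "How many men (a) and how many women (b) started RRT in 2016 against your advice".

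The statistics paragraph of section 2.3 promises description and graphs. It defines no rate, numerator or denominator. Section 1.2, discussing data from a large US health system, treats eGFR below 15 mL/min/1.73m² as an indication for dialysis, but the doctor form asks for no such count.

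**The concern.** The first decision that could differ by sex is whether the doctor regards the patient as end stage at all. Question 10 records the result of that decision. It is then the explicit base of question 12 and the natural base for the starts in question 9. If the label is given later or less often to women with the same kidney function, a comparison among labelled patients begins after the decision of interest has been made.

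The protocol's own background makes this plausible. Section 1.4 reports an adjusted eGFR at dialysis initiation 1.07 mL/min/1.73m² lower in women than in men, and section 1.5 an odds ratio of 1.70 for late start in women. Both are US findings about starts, not about labelling in Austrian clinics, so they support plausibility and nothing more.

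At stake is the reading of the result. Women judged to be in need could appear to be treated as often as men, or more often, while women in stage 5 are treated less often.

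**Working it through.** The plan gives no rate, sample size or expected difference for sub-study 3, so there is no figure to reproduce. The check below uses assumed counts.

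**Assumed inputs.** Each sex has 500 registered patients and 100 in stage 5. All men in stage 5 are labelled end stage; a share L of the women is. Among labelled patients 0.80 start RRT, 0.10 refuse and 0.10 have a shared decision to withhold. Unlabelled women start with probability u.

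**Formulas.** Men: Q10 = 100, Q9 = 80, Q12 = 10. Women: Q10 = 100L, Q9 = 80L + 100(1 − L)u, Q12 = 10L.

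**Step 1: starts.** For women, Q9/Q10 = 0.80 + u(1 − L)/L, against 0.80 in men. Starts per stage 5 patient are Q9/100 in women, against 80/100 in men.

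| L | u | Women Q9 / Q10 | Ratio women:men, Q9/Q10 | Ratio women:men, starts per stage 5 patient |
|---|---|---|---|---|
| 0.9 | 0 | 72/90 = 0.80 | 1.00 | 0.72/0.80 = 0.90 |
| 0.7 | 0 | 56/70 = 0.80 | 1.00 | 0.56/0.80 = 0.70 |
| 0.5 | 0 | 40/50 = 0.80 | 1.00 | 0.40/0.80 = 0.50 |
| 0.7 | 0.1 | 59/70 = 0.84 | 1.05 | 0.59/0.80 = 0.74 |
| 0.9 | 0.3 | 75/90 = 0.83 | 1.04 | 0.75/0.80 = 0.94 |
| 0.7 | 0.3 | 65/70 = 0.93 | 1.16 | 0.65/0.80 = 0.81 |
| 0.5 | 0.3 | 55/50 = 1.10 | 1.38 | 0.55/0.80 = 0.69 |

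With u = 0 the under-labelling is masked. With u above 0 the ratio points the other way, and in the last row it exceeds 100%.

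**Step 2: selective labelling.** Reversal does not need u above 0. Let L = 0.7 and u = 0, and suppose the 30 unlabelled women would have started with probability 0.5 had they been labelled. The 70 labelled women then supply 80 − 0.5 × 30 = 65 starts. Q9/Q10 is 65/70 = 0.93 (ratio 1.16), while starts per stage 5 patient are 0.65 v 0.80 (ratio 0.81).

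**Step 3: withholding.** Q12/Q10 = 10L/100L = 0.10 for every L, the same as 10/100 in men. The ratio is 1.00 throughout.

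**Step 4: rates per registered patient.** At L = 0.7 and u = 0, Q10/Q1 is 70/500 = 0.14 v 100/500 = 0.20, and Q9/Q1 is 56/500 = 0.112 v 80/500 = 0.16. Both ratios are 0.70, so a gap is visible. Now suppose instead that only 70 of the 500 women are in stage 5 and all are labelled. Then Q10 = 70, Q9 = 0.80 × 70 = 56 and Q11 = Q12 = 7, so questions 1 and 9 to 12 carry the same entries as before. A stage 5 count separates the two cases: the proportion judged end stage is 70/100 = 0.70 in the first and 70/70 = 1.00 in the second.

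**The case against.** **The plan defines no rates.** This stands. Only the restriction in question 12 is explicit; Q9/Q10 is an expected use, not a stated one.

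**Question 10 is a legitimate outcome.** The sub-study examines doctors' decisions, so asking for their judgement by sex is reasonable. Questions 4 to 8 also give measures by sex that do not depend on the label. This stands too, but question 10 as an outcome needs a base of comparable kidney function, and step 4 shows that registered patients do not supply one.

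**Unlabelled patients can still be counted.** A reader might infer that a woman never labelled end stage drops out of every later count, or that reluctance cancels out of every rate. The documents do not support this. Question 9 counts all starts and question 13 counts starts against advice, so both can include her. Rates with question 10 as numerator, or without it, would still show a gap. Exact cancellation of Q9/Q10 in the example also needs u = 0 and outcomes among labelled patients that do not depend on where the labelling threshold lies.

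**Stage 5 might be obtained by subtraction.** Question 1 minus the stages in question 2 leaves a remainder, but it also holds stage 1 and patients without a 2016 result, and it is fixed at the first result of the year. Question 3 is subdivided by stage but asks about laboratory checks and visits. Neither is a usable count of stage 5 patients.

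**The example builds in its result.** This stands: every input is assumed.

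**eGFR may carry its own sex bias.** This stands as a limitation. Section 1.4 says the female correction factors may be incorrect and reports an MDRD bias of −3.1 ± 17.2 mL/min/1.73m² in women under 65. That figure is not specific to values near 15, so its effect on a stage 5 count cannot be worked out from the documents.

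**Conclusion.** The point holds in a limited form. Need is counted only by the doctor's judgement, question 12 is conditional on it, and no laboratory count of stage 5 is collected to set against it. Q12/Q10, and Q9/Q10 if reported, can therefore mask or reverse under-labelling of women. Q10/Q1 and Q9/Q1 would show a gap that could not be separated from a difference in kidney function.

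The size is unknown. In the example with 70% of women labelled, Q9/Q10 gives a women-to-men ratio of 1.00 to 1.16 where starts per stage 5 patient give 0.70 to 0.81. These figures rest on the assumed labelling and start probabilities and show possibility only. A reader might infer that the survey is bound to report no sex difference. That does not follow, since it would require the analysts to report Q9/Q10 alone and disregard the other counts by sex. The change is worth making because it is cheap and addresses the mechanism that section 1.6 puts forward; the rest of the survey does not depend on it.

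**What to change.** Before the forms are distributed, add to the doctor form a count by sex of registered patients in stage 5 (eGFR below 15 mL/min/1.73m²) in 2016, taken from the laboratory record. State that it is a measurement denominator only and not a rule for starting treatment. State also which 2016 result counts: any result in the year matches the period of questions 9 to 12, but needs a different query from the first result used in question 2.

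Ask for two cross-counts by sex within that group: how many were judged end stage, and how many started RRT. Dividing the totals of questions 9 and 10 by the stage 5 count would not do, because those totals can include patients outside the group. In the statistics paragraph, name the denominator of each rate, report the two proportions by sex, and keep Q9/Q10 as a secondary ratio.

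The cost is three extra counts by sex per clinic and one further laboratory query. Clinics already tabulate laboratory stage by sex for question 2, are offered reimbursement, and are expected to hold meetings to agree their answers. The possible sex bias of eGFR should be stated as a limitation. The timing matters because section 2.3 has the questionnaires completed anonymously, so a count missing from the form would be hard to link to a clinic's other answers later.

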the hemodialysis population will be compared with that of the Austrian general population. Adjusted hazard ratios for the male-to-female mortality risk in hemodialysis patients, by region will be performed using Cox regression analysis. Statistical modeling will closely follow a previously published study of hemodialysis data, analyzed by sex and country/region.⁴ All obtained p-values will be considered exploratory in nature.

2.2 Description and analysis of sex-specific differences in treatment and outcomes in patients with chronic kidney disease.

Hypothesis:

There are sex-specific differences in treatment, length of hospitalization, mortality and dialysis initiation in patients with chronic kidney disease admitted to internal medicine wards.

Methodology:

Patients hospitalized at internal medicine wards of the Krankenanstaltsverbund (KAV) between Jan 1st 2015 and Dec 31st 2015 with eGFR <60 mL/min/1.73m will be included.

Primary study endpoints are length of hospital stay, death within hospitalization and dialysis initiation. Secondary endpoints are renal function parameters (eGFR, serum creatinine, blood urea nitrogen) and proteinuria during hospital stay. Laboratory data will be extracted from the KAV laboratory database and patient characteristics will be derived from the KAV patient management database.

Statistics:

Descriptive statistics will be used for presentation of demographic and clinical patient characteristics and prevalence of chronic kidney disease in women as compared to men.

Further statistical methods will be chosen according to data availability and quality: The present plans include logistic regression to calculate the male-to-female odds of reaching one of the endpoints, conditional logistic regression for pair-matched data or logistic regression with propensity scoring.

2.3 Descriptive analysis of decision-making by doctors and patients with regards to renal replacement therapy initiation

Hypothesis

There are sex-specific differences in decision-making of doctors and patients with end-stage renal disease with regards to renal replacement therapy initiation.

Methodology

Questionnaires will be sent to every Austrian chronic kidney disease outpatient clinic willing to participate. Doctors and patients will complete the questionnaire anonymously and questionnaires will be sent back after a 3 months-time period of data collection /questionnaire completion.

The following questions will be included in the questionnaire:

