3. My nationality is Austrian (a), Non-Austrian (b).
4. My native language is German (a), not German (b).
5. I am married (a), living with my partner (b), separated or divorced (c), single (d), widowed (e).
6. My highest level of education is less than high school.
7. I know the reason (a), don't know the reason (b) why my kidneys are weak or failing.
8. The most important reason why my kidneys are weak or failing, to the best of my knowledge is hypertension (a), diabetes (b), glomerulonephritis (c), polycystic kidney disease (d); another reason not mentioned here (e).
9. I come to the clinic seldom [once a year at the most] (a), frequently [at least 3 times a year] (b) in order to check my labs and/or discuss treatment and progression of my disease.
10. A doctor at this clinic has told me (a) has not told me (b) that I will likely need renal replacement therapy (RRT) within the next 12 months.
11. I already have (a) / don't yet have (b) a fistula or graft for vascular hemodialysis access.
12. A doctor at this clinic has informed me (a) has not informed me (b) about the possibility to undergo pre-emptive transplantation as an option for RRT.
13. A doctor at this clinic has informed me (a) has not informed me (b) about peritoneal dialysis as an option for RRT.
14. A doctor at this clinic has informed me (a) has not informed me (b) about the possibility to undergo hemodialysis as an option for RRT.
 1. I consider myself end stage and thus in need of undergoing RRT within the next 12 months.
15. RRT is not an option for me. I would rather die than go on dialysis.
16. I suffer from nausea/vomiting (a), fatigue/tiredness (b), edema (c), dyspnea (d).
17. I can take care (a), cannot take care (b) of my household.

Methodological Note: The questionnaire will be handed out to all patients coming to the outpatient clinic in the year 2017 by non-medical (administrative) personnel. The number of returned questionnaires will be counted and compared to the number of questionnaires that was handed out. Only the sex of the patient receiving the questionnaire will be recorded. The return of the questionnaire will be anonymous, by placing a box in the patient waiting area.

Statistics:

Data will be entered into an IBM SPSS statistics database. Descriptive analysis and graphical illustrations will be performed.

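### Patient questionnaire item 9 has no valid answer for someone who attends the clinic exactly twice a year, and anonymous return makes the gap irreparable afterwards

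*Combined protocol and SAP*

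**What the plan says.** The patient-level list in section 2.3 puts attendance in item 9: "I come to the clinic seldom [once a year at the most] (a), frequently [at least 3 times a year] (b". The options are labelled consecutively and nothing follows (b), so a middle option does not appear to have been lost in the text. No other patient item asks about visit frequency. At doctor level, question 3 asks each clinic how often its registered men and women had laboratory checks and saw the doctor in 2016, subdivided by stage.

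On timing, the Methodology paragraph says "questionnaires will be sent back after a 3 months-time period of data collection /questionnaire completion". The Methodological Note after the patient items says "The questionnaire will be handed out to all patients coming to the outpatient clinic in the year 2017". Calendar dates are not given. The survey goes out widely: "Questionnaires will be sent to every Austrian chronic kidney disease outpatient clinic willing to participate".

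On identification, the Note says "Only the sex of the patient receiving the questionnaire will be recorded" and "The return of the questionnaire will be anonymous, by placing a box in the patient waiting area". Response is judged by comparing forms returned with forms handed out. The analysis of this substudy is descriptive.

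**The concern.** The two options of item 9 leave a hole at two visits a year. A patient in that position can tick the nearer-sounding option or skip the item. A ticked box then looks like any other, and a blank cannot be told from an ordinary refusal. No name, code or linkage exists by which the clinic record could be consulted.

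Substudy 3 sets patients' answers side by side by sex. If men and women in the gap resolve it differently, the table will show a difference in follow-up frequency that reflects the form and not attendance. Any breakdown of other answers by follow-up frequency would have to rely on the same item.

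A smaller issue sits beside it. The plan states no rule of one form per patient, and a second form from the same person could not be recognised among the returns.

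**Working it through.** The plan gives no sample size, expected proportion or visit frequency for this survey, so there is no figure of its own to reproduce. The gap itself needs no assumption. Everything numerical after step 1 is illustration.

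**1. Mapping visits to options (item 9 as printed).**

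| Visits per year | Valid option |
|---|---|
| 0 or 1 | (a) |
| 2 | none |
| 3 or more | (b) |

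**2. Share with no valid answer.** Let p2 be the proportion attending exactly twice and p3 the proportion attending three or more times. The share with no valid answer is p2. If p2 were 10% to 40% (assumed), that share would be 10% to 40%.

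**3. Effect on the reported share choosing (b).** Let f be the fraction of twice-yearly attenders who tick (b). If all of them tick something, reported (b) = p3 + p2 × f. Assume 30% attend once, 30% twice and 40% more often, so the true share is 40%.
- f = 0: 0.40 + 0.30 × 0 = 40%.
- f = 1: 0.40 + 0.30 × 1 = 70%.
- All twice-yearly patients skip: 0.40 / (1 − 0.30) = 57% of the answers given.

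**4. Effect on the sex comparison when attendance is the same in men and women.** False difference = p2 × (f in men − f in women).
- Assume f = 0.6 in men and 0.4 in women. Men: 0.40 + 0.30 × 0.6 = 58%. Women: 0.40 + 0.30 × 0.4 = 52%. The false difference is 6 points.
- Same f values, p2 = 10%: 0.10 × 0.2 = 2 points. With p2 = 40%: 0.40 × 0.2 = 8 points.
- Equal f in both sexes: 0 points, whatever p2 is.

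**5. Can doctor-level question 3 fill the gap?** It gives totals per clinic, for 2016, by sex and stage. The patient forms are filled in during 2017 by unidentified individuals. The totals give context on attendance by sex but cannot tell which option a given patient should have ticked.

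**6. Collection period.** Three months and calendar year 2017 can both be true if the three months lie inside 2017. The doctor-level text fits this, since "this plan should encompass several meetings with the outpatient clinic doctors in early 2017". What is missing is the dates.

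**7. Repeat forms.** With v visits a year, a second visit falls inside a three-month period as follows.
- Even spacing, up to four visits a year: 0% of patients.
- Random timing: 1 − 0.75^v − v × 0.25 × 0.75^(v−1). This gives 6% for v = 2 and 26% for v = 4.

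These are chances of a second visit. A second form follows only if staff hand one out.

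**The case against.** The best counter-argument is that little hangs on item 9. The hypothesis of this substudy is "There are sex-specific differences in decision-making of doctors and patients with end-stage renal disease with regards to renal replacement therapy initiation", and the items on being told about, informed of or refusing renal replacement therapy bear on it more directly than a background question about attendance. Doctor-level question 3 already covers visit frequency by sex. The analysis is descriptive, and the time table schedules questionnaire testing before distribution, where such a gap might be noticed. All of this stands as a reason to rate the matter as minor. None of it supplies an answer for the twice-yearly attender, and testing guarantees the repair only if someone looks for it.

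Three stronger readings are tempting, and the documents do not support them.
- A reader might infer that the sex comparison is biased. That would need twice-yearly men and women to answer differently, and nothing in the documents shows that they would. The 6-point figure comes wholly from an assumed 60% against 40%.
- A reader might infer that the two statements of the collection period contradict each other. They are compatible and lack only dates.
- A reader might infer that a form is handed out at every visit. The plan does not say so, and handing forms to all patients most naturally means one each. With evenly spaced visits, up to four a year, a three-month period produces no repeats at all.

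**Conclusion.** Item 9 is defective as written: exactly two visits a year has no valid answer, and the resulting misclassified or missing responses cannot be recovered after anonymous return. This rests on the printed options alone.

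The size is unknown. The affected share equals the proportion attending twice a year, for which the documents give no figure, either overall or among patients with end-stage disease. The illustrations run from no false sex difference, when the sexes answer alike, to 2 to 8 points under the assumed ticking behaviour and twice-yearly shares of 10% to 40%.

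The undated collection period and the missing one-form rule are points for clarification, not errors. The consequence is limited to the descriptive patient survey in substudy 3; the registry and hospital substudies are untouched. Severity is minor.

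**What to change.** Before distribution, make the options of item 9 exhaustive: at most once, twice, or three or more times a year. A count of visits in the past 12 months would serve equally well. The cost is one answer option or one reworded line, and the testing step in the time table is the natural place for it.

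As a minor clarification, state the dates of the three-month period within 2017 for all clinics, and give each patient one form at the first visit in that period. Alternatively, add a yes/no item asking whether the patient has already returned this form, and set repeats aside. The added item leaves the rule on recording only sex unchanged, but it relies on honest self-report, and it cleans the returned forms without correcting the hand-out count. If neither is adopted, label the response rate as per form and not per patient. These changes cost one or two sentences and at most one extra item.

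No weighting for visit frequency is needed: the survey is descriptive, and the documents give no visit frequencies on which to base weights.

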1.5 Late dialysis initiation and poor kidney disease awareness among women

Kausz et al. have shown as early as 2000 that among those 23% of patients who began dialysis late in the United States between 1995 and 1997 (i.e. glomerular filtration rate $<5 \text{ ml/min}/1.73\text{m}^2$), women had an odds ratio of 1.70 compared with men, surpassing that of Hispanics and Asians (compared with Caucasians), uninsured patients (compared with private insurance), and employed patients (compared with unemployed).²³ These data are consistent with more recent results.^{24, 25}

Coresh et al. analyzed chronic kidney disease awareness among US adults using NHANES surveys conducted in 1999 to 2000 and found that less than one fifth ($18.6 \pm 6.3\%$) of adults with chronic kidney disease stage 3 and albuminuria ($>30 \text{ mg/g}$ creatinine) reported previous knowledge/diagnosis of weak or failing kidneys. Among

those in chronic kidney disease stage 3 but without proteinuria, less than one tenth ($8.2\pm2.3\%$) of adults were aware of their chronic kidney disease. In the latter group, awareness levels were significantly lower among women ($2.9\pm1.6\%$ awareness in women versus $17.9\pm5.9\%$ awareness in men).²⁶ This observation might explain the potential under-representation of women in chronic kidney disease clinics (Figure 1).

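### The patient questionnaire cannot tell a first visit from established attendance, so a sex difference on items 10 and 12–14 may reflect time under care and not what doctors tell men and women

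*Combined protocol and SAP*

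**What the plan says.** The Methodological Note in Section 2.3 defines who receives the form: "The questionnaire will be handed out to all patients coming to the outpatient clinic in the year 2017 by non-medical (administrative) personnel". First attenders are not excluded. Completed forms are returned anonymously, "by placing a box in the patient waiting area", and the recipient's sex is the only thing recorded at hand-out.

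Four patient-level items concern information given by the clinic's doctors: item 10 (likely need for renal replacement therapy, RRT, within 12 months), item 12 (pre-emptive transplantation), item 13 (peritoneal dialysis) and item 14 (hemodialysis). Each has two answers and is limited to doctors at the clinic in question. Item 13 is typical: "A doctor at this clinic has informed me (a) has not informed me (b) about peritoneal dialysis as an option for RRT". Item 11 sits among them but asks something else, namely vascular access status: "I already have (a) / don't yet have (b) a fistula or graft for vascular hemodialysis access".

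The only item on attendance is item 9, which asks about frequency: "I come to the clinic seldom [once a year at the most] (a), frequently [at least 3 times a year] (b". No item asks for the date of first attendance, its duration, or whether this is a first visit.

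The Statistics paragraph of Section 2.3 plans descriptive and graphical analysis and names no stratification. The hypothesis is that decision-making by doctors and patients about starting RRT differs by sex.

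**The concern.** Whether a patient has been told something by a clinic's doctors depends on how those doctors behave and on how much opportunity they have had. The form measures the combined result and records nothing about opportunity. Someone who registered that morning and someone followed for years answer the same two-option question.

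Items 10 and 12–14 are the only patient-reported measure of how doctors inform men and women, and Section 1.6 raises the possibility that doctors are more reluctant to start RRT in women. A lower informed share in women would invite that reading. A larger share of recent arrivals among women would produce the same table. Because return is anonymous, nothing can be done about this once the forms are in the box.

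A sex difference in clinic contact is not far-fetched on the plan's own argument. Section 1.5, headed "Late dialysis initiation and poor kidney disease awareness among women", reports lower awareness in women (2.9% against 17.9% in stage 3 without proteinuria) and offers this as a possible reason for women's under-representation in CKD clinics. Awareness that affects whether women reach a clinic could also affect when they reach it.

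**Working it through.** **What the documents fix.** Sub-study 3 states no sample size, expected proportion or precision, so there is no figure of the plan's to reproduce. These facts come from the form and its Methodological Note:

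| Feature | In the plan |
|---|---|
| Recipients | all attenders, first visits included |
| Answers on items 10, 12, 13, 14 | two options, this clinic only |
| Duration or first-visit item | none; item 9 is frequency only |
| Linkage to clinic records | none; only sex noted at hand-out |
| CKD stage on the patient form | not recorded |
| Planned stratification | none stated |

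**How large the effect could be.** All inputs below are assumptions. Let *p* be the informed share among established patients and *q* the share among first-visit patients, each equal in the two sexes. Let *f* be the first-visit share, which may differ by sex. Then

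- informed share = (1 − *f*)·*p* + *f*·*q*
- gap, men minus women = (*p* − *q*)·(*f* women − *f* men)

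With *p* = 0.45, *q* = 0, *f* = 0.10 in men and 0.20 in women:

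- men: 0.90 × 0.45 = 0.405
- women: 0.80 × 0.45 = 0.360
- gap: 4.5 points
- odds ratio: (0.405/0.595) / (0.360/0.640) = 0.681/0.5625 = 1.21

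Other assumptions:

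| *p* | *q* | First-visit share, men v women | Men v women informed | Result |
|---|---|---|---|---|
| 0.45 | 0 | 10% v 15% | 40.5% v 38.25% | OR 1.10 |
| 0.45 | 0 | 5% v 20% | 42.75% v 36.0% | OR 1.33 |
| 0.60 | 0 | 10% v 20% | 54% v 48% | +6 points |
| 0.60 | 0.60 | 10% v 20% | 60% v 60% | 0 |
| 0.30 | 0.50 | 10% v 20% | 32% v 34% | −2 points |

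The last row represents new patients who arrive with advanced disease and are informed sooner. With *q* = 0, *p* from 0.3 to 0.9, and first-visit shares from 5% v 10% up to 10% v 30%, the gap runs from 0.3 × 0.05 = 1.5 points to 0.9 × 0.20 = 18 points. If first-visit patients are informed half as often as established ones, it runs from 0.75 to 9 points.

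**After the change.** Within a stratum of time since first visit, *f* drops out of the comparison. If doctors inform both sexes equally within that stratum, the gap from differing first-visit shares is zero by construction. In the central case both sexes show 45% among established patients.

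**The case against.** Several points against the concern are sound.

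- **When the form is filled in.** A reader might infer that first-visit patients are bound to answer that they have not been informed. The plan does not say whether completion comes before or after the consultation. A box in the waiting area suits a patient on the way out as well as one on the way in, and a new patient informed that day can say so. This stands. Even after the consultation, however, a patient seen once has had less opportunity than one followed for years.
- **Direction.** A reader might also infer that women are referred later and that this will pass for doctors withholding information. No section gives referral timing or length of attendance by sex. The awareness figures come from a US population survey and are used to explain women's possible absence from clinics, not shorter attendance by those who come. Starting dialysis at a lower eGFR (Sections 1.4 and 1.5) would, other things equal, lengthen women's time in clinic. This stands: the sign is unknown.
- **Interpretation.** The analysis is descriptive, the hypothesis covers patients as well as doctors, and nothing commits the sponsor to attributing a gap to doctors. This is true, but a descriptive sex contrast will still be read against the hypothesis.
- **Other data.** Doctor-level questions 4 and 6–8 count men and women informed, and questions 1–3 give registrations, stages and visit counts by sex. They offer a parallel view that does not depend on when a patient fills in a form. They are clinic totals, however, cannot be linked to patient answers, and do not measure time since first visit either. Patient item 9 is at best a partial proxy, and a first attender cannot properly answer it.

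**Conclusion.** The point holds as a limit on interpretation. As written, the form cannot separate a sex difference in time under care from a sex difference in doctors' informing on items 10, 12, 13 and 14, and the missing information cannot be recovered after anonymous return. Item 11 is not affected in this way, because a new patient can report vascular access accurately.

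The documents do not show that such a bias exists, or which sex it would favour. The 4.5-point gap and odds ratio of 1.21 rest wholly on assumed inputs: 45% of established patients informed, none at a first visit, and first-visit shares of 10% and 20%. The gap is zero if new and established patients are informed equally often, or if the first-visit share is the same in both sexes. It reverses if new patients are informed more often. This is a worthwhile, inexpensive improvement to the form; it does not show that the sub-study's result would be wrong.

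**What to change.** Before distribution, add one item to the patient form: *I first came to this clinic: today / within the last 12 months / 1–3 years ago / longer ago.* State in the Statistics paragraph of Section 2.3 that items 10, 12, 13 and 14 (not 11) will be tabulated by sex within these categories, with the *today* group shown separately and left out of the main sex contrast.

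State also that confounding by CKD stage remains. Stage bears on whether a talk about RRT is yet relevant, and the patient form does not record it, so the stratified contrast will not by itself isolate doctors' behaviour.

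The cost is one more tick-box and smaller cells in the stratified table. The Time Table already lists questionnaire development and testing, so the item fits there; it cannot be added once forms have been returned.
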